2.2.2 Key Secondary Endpoints

- All-cause mortality (defined as the fraction of patients that have died, regardless of cause, by the end of Day 90)
- Renal replacement therapy (RRT)-free days up to Day 30 (excluding patients on RRT for chronic renal failure at time of randomisation)
- Intensive care unit (ICU)-free days up to Day 30

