3.1 General Design Considerations

The overall adaptive design is a Phase 2b/3 trial, in which dose-ranging with response-adaptive randomization (RAR) (see Appendix 5 for details) is utilized in a first part (the Phase 2b part – Part 1), followed by a traditional 1:1 randomised comparison of selepressin to placebo in the second part (the Phase 3 part – Part 2). The final analysis uses patients from both parts of the trial. The entire trial, combining both parts, represents an adequate and well-controlled comparison of selepressin and placebo.

In Part 1 of the trial, up to four dosing regimens will be investigated.

Arm 1: Starting dose at 1.7 ng/kg/min, and a max. dose of 2.5 ng/kg/min

Arm 2: Starting dose at 2.5 ng/kg/min, and a max. dose of 3.75 ng/kg/min

Arm 3: Starting dose at 3.5 ng/kg/min, and a max. dose of 5.25 ng/kg/min

Arm 4: Starting dose at 5 ng/kg/min, and a max. dose of 7.5 ng/kg/min

Part 1 comprises a minimum of 300 evaluable patients and a maximum of 800 treated patients. During Part 1, patients will be randomised to placebo or selepressin (Arms 1 to 3). Arm 4 will only be opened between 200 evaluable- 600 treated patients and if there is at least a 50% probability that Arm 3 has a higher expected P&VFD than Arm 2 and if data from the lower dosing levels do not suggest any significant safety signals. To minimize the risk of imbalance between treatment arms, randomisation will be stratified based on trial site, the need for mechanical ventilation (Yes/No), norepinephrine/noradrenaline requirement at baseline (< or \ge 30 μ g/min) and creatinine (< or \ge 150 μ mol/L) (See Appendix 7 for details).

Part 1 will begin with a 200-patients treated "burn-in" period during which fixed randomisation across the treatment arms will be used (one-third of the patients randomised to placebo and two-ninths of the patients to each of the selepressin arms [Arms 1 to 3]). The factors described above will be used to stratify the randomisation.

After completion of the burn-in period, Part 1 will utilize response-adaptive randomisation to preferentially place patients into the arms that appear to have the maximum benefit with respect to the primary endpoint. A fixed fraction (one third) of patients will be randomised to placebo throughout Part 1 to ensure contemporaneous control patients are enrolled throughout the trial.

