9.2 Primary Endpoint

• Vasopressor- and mechanical ventilator-free days (P&VFDs) up to day 30

This composite endpoint is defined as the number of days (reported to one decimal place (0.0 to 30.0)) from start of treatment with the investigational medicinal product (IMP) [selepressin or placebo] to 30.0 days thereafter during which the patient is: 1) alive; 2) free of treatment with intravenous vasopressors; and 3) free of any invasive mechanical ventilation (see definition below).

Patient Death

By definition, any patient that dies within this 30-day period will be assigned zero P&VFDs, even if there is a period during which the patient is alive and free of both vasopressor treatment and mechanical ventilation.

Definition of "Free of Vasopressors"

Free of vasopressors means less than 60 minutes during any contiguous 24-hour period (regardless of calendar day). If a patient requires periods of vasopressors longer than 60 minutes in total during any 24-hour period, the intervening intervals during which they are free of vasopressors will not be included in the period free of vasopressors in the determination of the number of P&VFDs. Thus, the period free of vasopressors begins at the end of the last use of vasopressors that was either: 1) longer than 60 minutes in duration; or 2) part of greater than 60 minutes of use within a contiguous 24-hour period.

Norepinephrine/noradrenaline, phenylephrine, dopamine, epinephrine/adrenaline, vasopressin, terlipressin, and IMP (i.e. selepressin and placebo) all constitute a vasopressor for the purpose of the primary analysis.

Vasopressor use due to anaesthesia or procedure-induced hypotension during and up to three hours after a surgery or procedure (including bedside) is exempt from this rule (i.e. such use of vasopressors would not affect the calculation of P&VFDs).

Date: 20 Nov 2017 E-Statistical Analysis Plan-17877; Ver.9.0 Supersedes: Ver. 8.0

Page 24 of 80

Definition of "Free of Mechanical Ventilation"

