9.2.1 Primary Variable Analysis

The primary endpoint, P&VFDs, will be analyzed using a van Elteren test, stratified by need for ventilation (Yes/No), time from onset of shock (onset of any vasopressor) to start of treatment (< or \ge 6 hours), and norepinephrine/noradrenaline requirement at baseline (< or \ge 30 μ g/min).

The primary analysis will compare all patients on all selepressin arms from both parts of the trial (pooled together and treated as a single arm) to all patients on the placebo arm from both parts of the trial (see Appendix 7 for a discussion on treatment estimate bias).

The primary analysis will be a test of superiority using a two-sided 5% significance level test.

Treatment effects will be estimated assuming a negative binomial distribution (to allow for possible overdispersion in a Poisson distribution) for the quantity (30 minus P&VFDs) for survivors, and a binomial distribution to model the probability of surviving. Both models adjusted for need for ventilation (Yes/No), time from onset of shock to start of treatment (< or \geq 6 hours), and norepinephrine/noradrenaline requirement at baseline (< or \geq 30 µg/min) (see Appendix 3 for details). For completeness, the proportion of patients dying, and the P&VFDs for survivors will also be presented.

Page 26 of 80

Furthermore, P&VFDs will be tabulated by treatment arm (including pooled active treatment arms), and presented graphically by histograms and cumulative distributions functions.

The success (statistical/clinical significance) of the trial will be based upon the comparison of the analysis above (all patients on all selepressin arms from both parts of the trial (pooled together and treated as a single arm) compared to all patients on the placebo arm from both parts of the trial).

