Incidence of RRT will be analysed by a logistic regression model with time from onset of shock to start of treatment, baseline creatinine and norepinephrine/noradrenaline requirement at baseline (µg/kg/min) as covariates, and treatment and need for ventilation as factors. The 95% confidence interval for the difference in proportions between treatment groups will be constructed using the delta method (see Appendix 4 for details). Patients already on RRT for chronic renal failure at time of inclusion will be excluded from the analysis of incidence of RRT.

Non-inferiority will be claimed if the upper limit of the two-sided 95% CI of the adjusted difference in proportions is less than 20% of the estimated incidence of RRT in the placebo group. Superiority can be claimed (5) if the upper limit is less than 0.

I.e., let $\widehat{p_S}$ and $\widehat{p_P}$ be the estimated incidences of RRT in the combined selepressin groups and the placebo group respectively. Non-inferiority will then be claimed if

$$\widehat{p_S} - \widehat{p_P} + 1.96 * \sqrt{var(\widehat{p_S} - \widehat{p_P})} < 0.2 * \widehat{p_P}$$

and superiority will be claimed if

$$\widehat{p_S} - \widehat{p_P} + 1.96 * \sqrt{var(\widehat{p_S} - \widehat{p_P})} < 0$$

A forest plot including the non-inferiority tests for all analyses will be presented.

Furthermore, incidence of RRT will be tabulated by treatment arm (including pooled active treatment arms).

A subgroup analysis will be performed on patients without acute RRT at baseline.

9.3.1.9 Duration of RRT up to Day 90 (excluding patients on RRT for chronic renal failure at time of randomisation)

Duration of RRT is defined as the cumulative periods with RRT (continuous renal replacement therapy, intermittent hemodialysis or peritoneal dialysis) and will be analyzed excluding patients on RRT for chronic renal failure at time of randomisation.

For patients withdrawn or dying while still on RRT, the duration will be based on the data available up until the time of withdrawal or death.

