9.3.2 Morbidity/Mortality

9.3.2.1 Intensive Care Unit (ICU)-free Days up to Day 30

ICU -free Days up to Day 30 will be defined and analyzed in a similar manner as the primary endpoint, with the van Elteren test stratified by need for ventilation (Yes/No), time from onset of shock to start of treatment (< or \ge 6 hours), and norepinephrine/noradrenaline requirement at baseline (< or \ge 30 µg/min) and baseline creatinine (< or \ge 150 µmol/L).

A sensitivity analysis will be performed where the definition of time spent in the ICU will include first admission to emergency department, as some patients will be enrolled and have first IMP treatment in the emergency department.

9.3.2.2 ICU Length of Stay up to Day 30

ICU length of stay is defined as the cumulative periods spent in ICU from start of IMP to 30 days after.

For patients withdrawn or dying while still in ICU up to Day 30, the duration will be based on the data available up until the time of withdrawal or death.

ICU length of stay will be analyzed between treatment groups using the permutation test specified in Section 9.3.1.3 stratified by the combination of time from onset of shock to start of treatment (< or \ge 6 hours), baseline creatinine (< or \ge 150 μ mol/L), norepinephrine/noradrenaline requirement at baseline (< or \ge 30 μ g/min) and need for ventilation (Yes/No).

A sensitivity analysis will be performed where the definition of time spent in the ICU will include first admission to emergency department, as some patients will be enrolled and have first IMP treatment in the emergency department.

9.3.2.3 All-cause Mortality (Defined as the Fraction of Patients That Have Died, Regardless of Cause, by the end of Day 30, Day 90, and Day 180)

Mortality will be analysed by a logistic regression model with the individual SOFA scores and age as covariates and treatment arm as factor. The 95% confidence interval for the difference in proportions between treatment groups will be constructed using the delta method as for incidence of RRT (section 9.3.1.8). There will be no imputations for mortality.

Non-inferiority will be claimed if the upper limit of the two-sided 95% CI of the adjusted difference in proportions is less than 30% of the estimated incidence of mortality in the placebo group. Superiority can be claimed (5) if the upper limit is less than 0.

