And as can be clearly seen, the maximization of l_1 and l_2 with regards to β_1 does not depend on β_2 and vice-versa. Hence, β_1 and β_2 can be estimated separately from two independent models, i.e. a logistic regression for the probability of surviving, and a poisson regression (or negative binomial to allow for overdispersion) for the distribution of days on vasopressors and mechanical ventilation for those surviving.

In practice, and with the model adjusted for A, B and C, this means that the probability of surviving will be estimated from a logistic regression adjusted for A, B and C and treatment group. From each treatment group we can do an LSMEANS and get an 'overall' β_1 along with the standard error of β_1 .

For a given treatment group the mean probability of surviving is given as:

$$\frac{e^{\beta_1}}{1+e^{\beta_1}}$$

The distribution of days on vasopressors and mechanical ventilation (30- PVFD's) for those surviving will be estimated from a negative binomial regression (poisson with a potential overdispersion), also adjusted for A, B and C and treatment group. From each treatment group we can do an LSMEANS and get an 'overall' β_2 along with the standard error of β_2 .

For a given treatment group the mean PVFD's for survivors is given as:

$$(30 - e^{\beta_2})$$

The mean PVFD's for all subjects (survivors and non-survivors) is then given as:

$$\frac{e^{\beta_1}}{1 + e^{\beta_1}} * (30 - e^{\beta_2})$$

Let

$$f(\beta_1, \beta_2) = \frac{e^{\beta_1}}{1 + e^{\beta_1}} * (30 - e^{\beta_2})$$

Using the delta method we can calculate the variance of $f(\beta_1, \beta_2)$:

Page 55 of 80

$$f'(\beta_1, \beta_2) = \left(\left(30 - e^{\beta_2} \right) * \frac{e^{\beta_1}}{(1 + e^{\beta_1})^2} , \frac{e^{\beta_1}}{(1 + e^{\beta_1})} * \left(-e^{\beta_2} \right) \right)$$

Hence,

$$var[f(\beta_1,\beta_2)] = f'(\beta_1,\beta_2) \begin{pmatrix} \sigma_{\beta_1}^2 & 0 \\ 0 & \sigma_{\beta_2}^2 \end{pmatrix} f'(\beta_1,\beta_2)^t$$

$$= \left(\sigma_{\beta_{1}}^{2} * \left(30 - e^{\beta_{2}}\right) * \frac{e^{\beta_{1}}}{(1 + e^{\beta_{1}})^{2}} \quad \sigma_{\beta_{2}}^{2} * \frac{e^{\beta_{1}}}{(1 + e^{\beta_{1}})} * \left(-e^{\beta_{2}}\right)\right) \left(\frac{\left(30 - e^{\beta_{2}}\right) * \frac{e^{\beta_{1}}}{(1 + e^{\beta_{1}})^{2}}}{\frac{e^{\beta_{1}}}{(1 + e^{\beta_{1}})}} * \left(-e^{\beta_{2}}\right)\right)$$

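### The mortality model in SAP 9.3.2.3 adjusts for SOFA and age but for none of the randomisation factors, unlike the other key secondary analyses, and no reason is given

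*SAP*

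**What the plan says.** On allocation, SAP section 3.1 says "randomisation will be stratified based on trial site, the need for mechanical ventilation (Yes/No), norepinephrine/noradrenaline requirement at baseline" and creatinine. The cut-points are 30 µg/min for norepinephrine and 150 µmol/L for creatinine.

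On mortality, section 9.3.2.3 says "Mortality will be analysed by a logistic regression model with the individual SOFA scores and age as covariates and treatment arm as factor". The same model serves Days 30, 90 and 180. The key secondary among these is Day 90; section 2.2.2 lists "All-cause mortality (defined as the fraction of patients that have died, regardless of cause, by the end of Day 90"). The interval for the difference in proportions comes from the delta method. It decides superiority (upper limit below 0) and non-inferiority (upper limit below 30% of the estimated placebo rate).

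The comparable analyses are adjusted differently:

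- RRT-free days (9.3.1.7) and ICU-free days (9.3.2.1), the other two key secondaries, use a van Elteren test stratified by ventilation, time from onset of shock, norepinephrine and creatinine.
- The incidence of RRT counting deaths (9.3.1.8) has the same delta-method interval and the same form of claim rule as mortality: "Incidence of RRT will be analysed by a logistic regression model with time from onset of shock to start of treatment, baseline creatinine", followed by norepinephrine and need for ventilation.
- The effect estimate for the primary endpoint (9.2.1) has a survival and a days component: "Both models adjusted for need for ventilation (Yes/No), time from onset of shock to start of treatment", and for norepinephrine.

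**The concern.** When allocation is balanced on prognostic factors, a model that leaves them out does not take credit for that balance, and its standard error tends to be too large. The error is conservative, but it falls on a key secondary endpoint whose superiority and non-inferiority claims both rest on this interval. Mortality is also the only one of the three key secondaries without any of these factors. With no rationale given, a reader cannot tell whether the omission is deliberate or an oversight.

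**Working it through.** **Covariates side by side**

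| Analysis (SAP) | Ventilation | Norepinephrine | Creatinine | Time from onset | SOFA, age |
|---|---|---|---|---|---|
| Randomisation (3.1) | yes | yes | yes | no | no |
| RRT-free days (9.3.1.7) | yes | yes | yes | yes | no |
| ICU-free days (9.3.2.1) | yes | yes | yes | yes | no |
| RRT or death (9.3.1.8) | yes | yes | yes | yes | no |
| Mortality (9.3.2.3) | no | no | no | no | yes |

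Site is also a stratification factor, but none of these analyses uses it, so its absence is not peculiar to mortality.

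**The plan's own figure.** Section 9.3.2.3 gives 2-3% as what the 30% limit corresponds to at placebo mortality of 20-25%. Solve d + 1.96·√[p(1−p)/n_P + (p+d)(1−p−d)/n_S] = 0.3p with 1800 patients (section 3.2), split 900:900 as an assumption:

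- p = 0.20: √(0.0001778 + 0.0001921) = 0.01923; 1.96 × 0.01923 = 0.0377; d = 0.060 − 0.0377 = 0.022.
- p = 0.25: √(0.0002083 + 0.0002260) = 0.02084; 1.96 × 0.02084 = 0.0408; d = 0.075 − 0.0408 = 0.034.

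The 2-3% is therefore reproduced as the largest observed excess over placebo. Splits of 1000:800 and 1033:767 give nearly the same values. At equal rates the half-width is 1.96·√[2p(1−p)/900] = 3.7 points (p = 0.20) and 4.0 points (p = 0.25).

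**Effect of adding the factors.** The SAP gives no prognostic strengths, so these are assumptions. Trials of 1800 were simulated with 1:1 allocation within the eight strata, mortality 21-24%, treatment odds ratio 0.75 and 800 runs per setting. The risk difference was taken from LSMEANS with a delta-method SE. Selected settings:

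| OR of each factor given SOFA and age | Factor-SOFA correlation | SE, SOFA + age | SE, factors added | Cut | Power | Adjusted placebo rate |
|---|---|---|---|---|---|---|
| 1.0 | 0 | 0.0182 | 0.0182 | 0% | 64.6 → 64.9% | 20.5 → 20.4% |
| 1.3 | 0 | 0.0183 | 0.0182 | 0.5% | 69.0 → 68.6% | 20.8 → 20.5% |
| 1.6 | 0 | 0.0185 | 0.0182 | 1.6% | 67.0 → 68.1% | 21.2 → 20.5% |
| 2.0 | 0 | 0.0189 | 0.0183 | 3.2% | 62.4 → 64.7% | 22.1 → 20.5% |
| 1.6 | 0.4 | 0.0185 | 0.0183 | 1.1% | 65.9 → 66.4% | 21.2 → 20.5% |
| 2.0 | 0.4 | 0.0189 | 0.0184 | 2.6% | 62.5 → 65.6% | 22.0 → 20.5% |

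At correlation 0.8 the cut was at most about 1.6%. With no treatment effect, rejection was 4.2% and 5.4% without the factors and 4.6% and 5.4% with them, so neither model has a validity problem.

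A second set (500 trials per scenario; assumed odds ratios of 1.5 for ventilation, 1.8-2.5 for norepinephrine and 1.2-1.3 for time from onset) gave SEs of 0.0208 → 0.0206, 0.0202 → 0.0199, 0.0215 → 0.0210 and 0.0209 → 0.0204. These are cuts of 1.0 to 2.4%, with a power gain of at most 0.6 points.

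**In absolute terms.** A 3% cut in a half-width of 3.7 to 4.0 points is 0.03 × 3.7 = 0.11 to 0.03 × 4.0 = 0.12 points. In patients it is 1 − 0.97² = 5.9%, about 106 of 1800, at the top of the range and none at the bottom. At the mortality effects in section 3.2 (25% against 23.5% or 23%), unadjusted power with 900 per arm is only about 11% or 17%, so no covariate choice changes the prospects much.

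**Side effect on the margin.** The non-inferiority limit is 0.3 times the estimated placebo rate. In the table that rate falls by 0.1 to 1.6 points, so the limit falls by 0.3 × 0.1 = 0.03 to 0.3 × 1.6 = 0.48 points. In the strongest setting this exceeds the gain in half-width, 1.96 × (1.89 − 1.83) = 0.12 points.

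**The case against.** The strongest defence is that SOFA and age are a coherent prognostic set. Section 9.2.2 names them as example covariates for predicting death. The individual scores include cardiovascular, respiratory and renal components, the organ systems behind norepinephrine, ventilation and creatinine. In the simulations the SOFA and age model was also more precise than one with ventilation and norepinephrine alone (SE 0.0182-0.0189 against 0.0190-0.0195). This stands as a reason to keep SOFA and age, and it is why the gain may be close to zero. It does not explain why mortality alone omits the factors. The SAP does not define the modified score, so how far it replaces them cannot be settled here.

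It is also true that the SE of the log odds ratio rises slightly when the factors are added (0.119-0.120 to 0.123-0.124). The claims in 9.3.2.3 rest on the risk difference, where the SE did not rise.

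A reader might infer something stronger: that the report will hold two conflicting adjusted Day-30 mortality effects, since the primary endpoint has its own 30-day survival model (Appendix 3: "the probability of surviving will be estimated from a logistic regression adjusted for A, B and C and treatment group"). The documents do not support this. Appendix 3 uses that model only as a step towards mean P&VFDs and specifies no survival difference, interval or test. Section 9.2.1 adds only a presentation of the proportion dying. The simulated risk differences from the two models were also nearly equal on average, about −0.043 each. The key secondary is Day 90, for which there is a single model.

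**Conclusion.** The point holds as a minor improvement. The mortality model omits every factor used to stratify randomisation, the two other key secondaries and the RRT-or-death model do not, and the SAP gives no reason. The interval for the risk difference may be slightly too wide: about 0 to 3% in the SE, with power changing by about −0.5 to +3 points, the low end being simulation noise.

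This rests on assumed odds ratios, assumed correlations with SOFA and the planned 1800 patients. The SAP records that the trial ended for futility, so the achieved sample will be smaller and absolute widths larger; the percentage cut should depend little on sample size. It would be tempting to say that precision is certainly being thrown away. No figure in the SAP shows that, and the SOFA components may already carry much of the information. Type I error and the validity of the planned analysis are not in question.

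**What to change.** In SAP 9.3.2.3, keep the individual SOFA scores and age, and add need for ventilation, baseline norepinephrine requirement and baseline creatinine at Days 30, 90 and 180. Add time from onset of shock as well, to match 9.3.1.8; it is not a randomisation factor. If the shorter model is preferred, state why. If the plan can no longer be changed, report the extended model as a sensitivity analysis.

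The cost is wording only, since every variable is already used elsewhere in the SAP. At 20-25% mortality, 1800 patients give 360 to 450 deaths. Five SOFA scores, age, treatment and four added terms make 11 coefficients, so there are at least 360/11 ≈ 33 deaths for each. The one downside is the small shift in the adjusted placebo rate and the relative margin shown above; the text should say that the margin uses the placebo rate from the extended model.

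Leave the survival component in Appendix 3 unchanged. Its covariates match the van Elteren strata of the primary test and those of the days component, and changing it alone would break that match.

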9.3 Secondary Endpoints

For the purpose of a possible label inclusion, the Hochberg procedure (4) for adjustment on multiplicity will be implemented to selected key secondary endpoints. Only if the primary efficacy analysis leads to a statistically significant result at the (one-sided) 2.5% level, then the Hochberg procedure which is described below is applied to selected key secondary analyses. If the primary efficacy analysis does not result in statistical significance at the (one-sided) 2.5% level, then statistical significance (for the purpose of a possible label inclusion only) will not be declared for any of the key secondary analyses, regardless of their p-values.

The selected key secondary endpoints aimed at further demonstrating treatment effect are:

- All-cause mortality (defined as the fraction of patients that have died, regardless of cause, by the end of Day 90)
- Renal replacement therapy-free days up to Day 30 (excluding patients on RRT for chronic renal failure at time of randomisation)
- ICU-free days up to Day 30

In this application of the Hochberg procedure there are three hypothesis tests of superiority for each of the selected secondary endpoints. The target alpha level is (one-sided) 2.5%. The Hochberg procedure is as follows:

- Order the p-values from the smallest to the largest value, p(1) < p(2) < p(3), with corresponding null hypothesis $H_{(1)}$, $H_{(2)}$, and $H_{(3)}$.
- Start with the highest p-value. If p(3) < 2.5% (one-sided), then stop and declare all three comparisons significant at the 2.5% (one-sided) level (i.e. reject H₍₁₎, H₍₂₎, and H₍₃₎). Otherwise, accept H₍₃₎ for the endpoint related to p(3), and go to p(2) the second highest p-value.
- If p(2) < 2.5/2 = 1.25% (one-sided), then stop and declare significance for $H_{(1)}$ and $H_{(2)}$. Otherwise, accept $H_{(2)}$, for the endpoint related to p(2), and go to p(1) the lowest p-value.
- If p(1) < 2.5/3 = 0.833% (one-sided), then stop and declare significance for $H_{(1)}$. Otherwise, accept $H_{(1)}$, for the endpoint related to p(1).

Regardless of the statistical significance declared according to the Hochberg procedure, all analysis will be included and presented in the statistical report.

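### Section 9.3.2.3 lets Day-90 mortality superiority be claimed from an unadjusted 95% CI and does not say how that claim relates to the Section 9.3 gate and Hochberg procedure

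*SAP*

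**What the plan says.** Section 9.3 lists three key secondary endpoints under a Hochberg procedure, the first being "All-cause mortality (defined as the fraction of patients that have died, regardless of cause, by the end of Day 90". The procedure is conditional: "Only if the primary efficacy analysis leads to a statistically significant result at the (one-sided) 2.5% level" is it applied. If the primary fails, "then statistical significance (for the purpose of a possible label inclusion only) will not be declared for any of the key secondary analyses". The ordered one-sided thresholds are 2.5%, 1.25% and 0.833%. The section adds that all analyses will be presented whatever Hochberg yields. It then says that the pooled selepressin versus placebo comparison determines success for the secondary endpoints, which it describes as statistical and clinical significance. The label restriction is not repeated there.

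Section 9.3.2.3 covers mortality at three times ("Died, Regardless of Cause, by the end of Day 30, Day 90, and Day 180"). It gives a non-inferiority rule and then a superiority rule on the same covariate-adjusted interval: "Superiority can be claimed (5) if the upper limit is less than 0". The formula that follows puts it more firmly: superiority will be claimed when the estimate plus 1.96 standard errors is below 0. The section refers to neither the primary result, nor Hochberg, nor Section 9.3.

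Section 9.3.1.8 has the parallel rule for incidence of RRT, with the same formula introduced by "and superiority will be claimed if". RRT incidence is not a key secondary endpoint.

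**The concern.** Day-90 mortality is subject to two decision rules that use different thresholds and different preconditions, and the SAP does not rank them. One result can satisfy Section 9.3.2.3 and fail Section 9.3. Because the gate is worded as a label rule and the CI rule as a superiority claim, a report could present mortality superiority as pre-specified after a failed primary and cite Section 9.3.2.3 in support.

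Mortality superiority is the strongest efficacy statement this trial could make. The situation is also not hypothetical: Section 1 records termination for futility, and Section 9.1 says that data from a trial stopped for futility are analysed as planned. A non-significant primary is then the likely outcome, and that is where the two rules diverge most.

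**Working it through.** **1. The SAP's own thresholds.** Hochberg with three endpoints at one-sided 2.5%:
- 0.025/1 = 2.5% (z = 1.96)
- 0.025/2 = 1.25% (z = 2.24)
- 0.025/3 = 0.833% (z = 2.39)

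These match Section 9.3.

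**2. Level of the CI rule.** The criterion is estimate + 1.96 × SE < 0, so the one-sided level is 1 − Φ(1.96) = 0.0250, whatever the primary or the other key secondaries show.

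**3. Where the rules differ for Day 90.**

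| Primary | Day-90 mortality, one-sided p | Section 9.3.2.3 | Section 9.3 (label) |
|---|---|---|---|
| Not significant | < 0.025 | Superiority claimed | Nothing declared |
| Significant | 0.00833 to 0.025 | Superiority claimed | Depends on the other two p-values |
| Significant | < 0.00833 | Superiority claimed | Declared |

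**4. The thresholds as observed differences.** Solve d = z × √[pP(1 − pP)/nP + pS(1 − pS)/nS] with pS = pP − d. Inputs: N = 1800 (Section 3.2 and Appendix 6) and placebo mortality of 20-25% (the illustration in Section 9.3.2.3). With 800 patients in Part 1 at one third placebo and 1000 in Part 2 at 1:1, placebo has about 267 + 500 = 767 patients and selepressin 1033.

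| Placebo/selepressin | Placebo mortality | CI rule (z = 1.96) | 1.25% step | 0.833% step |
|---|---|---|---|---|
| 767/1033 | 25% | 3.95 points | 4.50 | 4.79 |
| 767/1033 | 20% | 3.62 | 4.12 | 4.39 |
| 900/900 to 600/1200 | 20-25% | 3.6-4.2 | 4.1-4.7 | 4.3-5.1 |

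The last row brackets the possible splits. A trial stopped early has fewer patients, so every figure would be larger. When the primary fails, no observed difference meets Section 9.3.

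**5. How often the rules part under a global null.** Take a four-variate normal for the primary and the three key secondaries, with a common correlation ρ. The SAP gives no correlation, so ρ is an assumption and is varied (2 million draws for each value).

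| ρ | CI rule claims Day-90 superiority | Gate plus Hochberg declares it | Share of CI claims not declared |
|---|---|---|---|
| 0 | 2.5% | 0.02% | 99% |
| 0.3 | 2.5% | 0.11% | 96% |
| 0.5 | 2.5% | 0.25% | 90% |
| 0.7 | 2.5% | 0.54% | 79% |

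Most of the gap is the failed-primary case. At ρ = 0 it is 0.975 × 0.025 = 2.4% of trials.

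**6. Illustration across the endpoints that carry a CI-based superiority rule.** The SAP gives no Day-90 or Day-180 rates, so all rates here are assumptions. For nested deaths the correlation is √[pA(1 − pB)/(pB(1 − pA))]. At 25%, 32% and 36% for Days 30, 90 and 180, it is 0.84 (Day 30 with Day 90), 0.77 (Day 30 with Day 180) and 0.92 (Day 90 with Day 180). The chance of at least one false mortality superiority claim is then about 4.5%. Adding RRT-or-death at 40%, with RRT independent of later death among Day-30 survivors, gives about 6.0%. Over other plausible rates the ranges are about 4-5% and 5-7%. Three independent tests would give 1 − 0.975³ = 7.3%.

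**The case against.** The case against is strong on several points.

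- **Label wording.** Section 9.3 limits the gate to label inclusion twice. A reader might infer that the SAP contradicts itself, with one result both claimed and not significant. The text does not support that. A label-level declaration and an endpoint-level statement at the nominal level can coexist. This part of the objection stands.
- **Position in the document.** Section 9.3.2.3 lies inside Section 9.3, whose general rule names Day-90 mortality. The other two key secondaries do not repeat the gate either. But their sections only specify a test. The mortality section states its own claim rule, so silence there matters more. The citation of guidance on switching between non-inferiority and superiority explains why the rule exists, not how it fits the gate.
- **Other endpoints.** Day-30 and Day-180 mortality and RRT incidence lie outside the Hochberg family, so nothing conflicts for them. A reader might set the 4-5% and 5-7% figures against the 2.5% target. That would be wrong, because the SAP sets that target for Day-90 mortality, RRT-free days and ICU-free days, and sets none for this other group. This also stands.
- **Error control.** It would be too strong to say that there is none. Each comparison is held at one-sided 2.5%. What is missing is control across endpoints and dependence on the primary.

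The objection does not remove the main difficulty. The SAP says that superiority will be claimed, never says what such a claim means outside the label, and elsewhere in Section 9.3 refers to statistical and clinical significance of secondary endpoints without the label limit.

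**Conclusion.** The point holds as one of undefined scope, confined to Day-90 mortality. Section 9.3.2.3 gives a standing superiority rule at one-sided 2.5%. Section 9.3 gives a gated rule at 2.5%, 1.25% or 0.833% for label purposes. Nothing says which one governs a superiority claim made outside the label, so a pre-specified mortality claim survives a failed primary.

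Under a global null the CI rule makes that claim in 2.5% of trials, against about 0.02% to 0.5% under gate plus Hochberg, so 79% to 99% of CI-rule claims would not be declared under Section 9.3. These figures rest on the assumed equal correlation of 0 to 0.7. The existence of the gap needs no assumption, since it follows from the two rules as written.

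The figures across Days 30, 90 and 180 and RRT incidence (about 4-5% and 5-7%) are illustrations under assumed event rates and do not measure the Day-90 problem. No sample size or power figure is affected.

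**What to change.** Add to Section 9.3.2.3 that a confirmatory claim of Day-90 mortality superiority requires a significant primary and rejection under the Section 9.3 Hochberg procedure. Add there and in Section 9.3.1.8 that CI-based superiority statements for Day-30 and Day-180 mortality and for RRT incidence, and for Day-90 mortality when the gate is closed, are nominal and support no confirmatory claim.

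The cost is two sentences and fewer possible claims if the primary fails. No model, interval, data collection or sample size changes, and all the intervals can still be reported. The SAP addendum, written after the futility stop and before unblinding, would have been a suitable place for the clarification.
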